## **10. Monitoring and Quality Assurance**

### 10.1 Oversight

General oversight of this project will be performed by the principal investigators (Drs. [name] and [name]) and will occur throughout the study period. Study staff will be trained in appropriate study protocols and procedures and will assist in ensuring the study adheres to the IRB-approved protocol.

### 10.2 Monitoring Plan

We plan to use a centralized Institutional Review Board (IRB) and a Data Safety Monitoring Board (DSMB) for all aspects of this research. Drs. [name] and [name] are the project PIs at MGB. Advocate Aurora Health (AAH) will cede review to MGB Institutional Review Board, and the MGB IRB will serve as the centralized IRB of record for this trial.

We will establish an independent data and safety monitoring board (DSMB). A DSMB is a requirement for all NIH funded Phase III trials. The DSMB will act in an advisory capacity to the NIH to monitor participant safety and evaluate the progress of the study, review procedures and management of the study. The DSMB reports will be shared with the project and local site PIs within 72 hours of their completion. The DSMB will consist of individuals with experience in quality of care, patient safety, and statistics. The DSMB will meet regularly, either in person, by teleconference call, or via email at the discretion of the DSMB chair, to review data related to the study protocols and ensure protection of patient confidentiality and safety, as well as to monitor the quality of the data collected via the study protocols. Compliance of regulatory documents and study data accuracy and completeness will be maintained through an internal study team quality assurance process.

This trial will be registered with [clinicaltrials.gov](https://clinicaltrials.gov).

### 10.3 Adverse events and unanticipated problems

The PIs and study team will meet on a regular basis throughout the study period and will be in direct contact with AAH clinical leadership involved in the project to obtain ongoing feedback.

De-identified study data will be accessible at all times for the MGH PIs and coinvestigators to review, if applicable. We will also ensure that all protocol deviations for the pilot study are reported to the NIH and the IRB according to the applicable regulatory requirements. Compliance of regulatory documents and study data accuracy and completeness will be maintained through an internal study team quality assurance process.

#### *10.3.1 Definition:*

**Adverse Event (AE):** Any untoward or unfavorable medical occurrence in a human study participant, including any abnormal sign (e.g. abnormal physical exam or laboratory finding), symptom, or disease, temporally associated with the participants' involvement in the research, whether or not considered related to participation in the research.

- Adverse Events will be classified using the following rating scales:
  - Severity: Mild, Moderate or Severe
    - Mild: Awareness of signs or symptoms but are easily tolerated
    - Moderate: Events introduce a low level of inconvenience or concern but may interfere with daily activities but are usually improved by simple therapeutic measures.
    - Severe: Events interrupt the participants' normal daily activities and generally require systemic drug therapy
  - Expectedness: Unexpected or Expected
    - Unexpected: nature or severity of the event is not consistent with the condition under study
    - Expected: event is known to be associated with the intervention or condition under study.

**Serious Adverse Event (SAE):** Any adverse event that:

- results in death
- is life threatening, or places the participant at immediate risk of death from the event as it occurred
- requires or prolongs hospitalization
- causes persistent or significant disability or incapacity
- results in congenital anomalies or birth defects
- is another condition which investigators judge to represent significant hazards.

#### *10.3.2 Determination*

Given the minimal risk nature of the study which aims to increase guideline concordant care for patients with persistently elevated blood pressures, we do not anticipate any SAEs or AEs. Patients' own primary care physicians will have ultimate decision-making authority for prescribing choices, as they would in routine clinical practice, and we expect any adverse events related to hypertension medication intensification, such as hypotension or bradycardia, to be the same or less as those experienced in routine clinical care, given the focus on patients with uncontrolled hypertension. For example, in the SPRINT trial, which tested intensive BP control among patients age 75 or older, similar rates of serious adverse events occurred in the intensive-treatment group and in the standard-treatment group. In this study, we are using standard blood pressure targets and include a younger patient sample who have persistently elevated blood pressure.

#### *10.3.3 Reporting*

As previously described, any adverse events as part of this study are expected to be similar, or lower, than those anticipated in routine hypertension care. The study team will not be providing any direct care to patients and all treatment decisions will ultimately be made by the patients' medical teams at Advocate Aurora Health. Any adverse event will be handled in the course of regular clinical care. Because we are not directly intervening upon patients and will have no patient contact during this study, prospectively tracking adverse events is infeasible. However, physicians will have contact information for our research team to report any concerns, and we will be in regular contact with practice and AAH leadership to monitor for any adverse events that come to attention through any of those channels. Therefore, while we will not be actively monitoring the occurrence of adverse events, which if done would require patient contact and detailed patient-level chart-reviews, we anticipate that the study team will be informed of any AEs or SAEs that do occur. [name], cardiologist practicing at AAH, with support by [name], research manager at AAH, are engaged in support of this project and will help with monitoring of physician feedback that gets routed through traditional departmental channels.

If we become aware of any AEs or SAEs throughout the course of the study, we will collect this information. Any reports of deaths will be submitted to the NIH Program Officer within 24 hours. Any unexpected SAEs will be reported to the NIH PO and the IRB within 48 hours of the study's knowledge of the SAE. All other reported SAEs and AEs received by the study team will be reported to the NIH Program Officer quarterly, unless otherwise requested by the DSMB.

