## **7. Risks and Discomforts**

We believe that the risks to participation for both physicians and patients are no more than minimal for several reasons. First, the interventions aim to emphasize guideline-recommended treatments for patients with persistently elevated blood pressure. Second, all treatment decisions will ultimately be made by licensed primary care physicians. Finally, the intervention is physician-focused and delivered through interventions that use information already available to physicians that is also guideline concordant and intended to reduce disparities in care. We believe there is no more than minimal risk

involved to the physician subjects, as the physicians will simply be given tools to alter their behaviors towards guideline recommended care. All medical decisions are ultimately made by the physician. This trial will not interfere with the ordinary workings of the primary care practices.

There is a small risk associated with altering hypertension medication prescribing, including hypotension, bradycardia, allergic reactions, and other adverse effects. However, in prior trials that increase intensification of blood pressure regimens, the risks have been similar in intervention and control arms. We believe the potential risks of treatment intensification as part of this trial are the same, or less than what is encountered during routine, guideline-concordant hypertension care, given the focus on patients with persistently elevated blood pressure. Final prescribing decisions will always be at the discretion of the patient's PCP.

Another potential small risk to patients will be privacy of health information. We will minimize the risk to privacy by taking appropriate steps to limit access to data to study investigators. Clinical data on the care for patients will be retrieved from the electronic medical records.

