Advocate investigators will extract data that contains patient health information (PHI) including MRN, first name, last name, date of birth, encounter dates, and Zip Codes. To protect against the risk of inappropriate disclosure of personal health information, only limited data will be shared with study collaborators at Mass General Brigham (MGB) who will oversee and conduct the analysis with insights from the Advocate team. The only PHI that will be shared with the BWH study investigators outside of Advocate are dates (e.g., date of birth, admission/discharge dates, and dates of medication fills), which are necessary to evaluate exposures and outcomes retrospectively. No other study investigators outside of BWH will receive any PHI. Advocate will then disclose HIPAA-limited datasets encrypted by a study key only known to the Advocate investigators to conduct the analyses. These datasets will consist of structured information from the EHR. Sharing this information will be necessary to assess the impact of the interventions.

The electronic data stored at Advocate will be safeguarded by state-of-the-art security protocols. All patient-specific information will be collected by querying Advocate's inpatient and outpatient databases; inpatient data will be necessary to evaluate outcomes such as hospitalizations. Identified patient information will be recorded on a password-protected electronic spreadsheet, with each patient assigned a specific study number. All identifiers (excluding dates) linked to study numbers will be locked and stored separately from the data analysis spreadsheet. The coded spreadsheet will also be stored on a password-protected computer in a locked office with access limited to study investigators only. Only the limited dataset will be utilized for analyses. All identifiers will be destroyed after completion of data analysis. Only study team members will have access to study related documents. All investigators have completed CITI training.

Mass General Brigham (MGB) has computer networks in place that employ up to date virus protection software and enable password-protected access only to study investigators. All data transfers between the organizations will be accomplished using secure file transfer protocols. To ensure the confidentiality

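### Harms rest on passive reports alone, and no by-arm hospitalization comparison is prespecified although inpatient data are already planned for extraction

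*Combined protocol and SAP*

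**What the plan says.** Section 7 names the foreseeable harms: "There is a small risk associated with altering hypertension medication prescribing, including hypotension, bradycardia, allergic reactions, and other adverse effects". Section 10.3.2 nevertheless states that "we do not anticipate any SAEs or AEs" and expects medication-related events to be no more frequent than in routine care, citing an earlier trial of intensive blood pressure control.

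Section 10.3.3 sets out how harms would be learned of. Its reason for not tracking them is that the team "will have no patient contact during this study, prospectively tracking adverse events is infeasible". On active monitoring it says: "while we will not be actively monitoring the occurrence of adverse events, which if done would require patient contact and detailed patient-level chart-reviews". Two channels remain. One is that "physicians will have contact information for our research team to report any concerns", and the other is regular contact with practice and health-system leadership. The commitment to collect is conditional: "If we become aware of any AEs or SAEs throughout the course of the study, we will collect this information".

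Section 11 describes a different source. Inpatient and outpatient databases will be queried, and "inpatient data will be necessary to evaluate outcomes such as hospitalizations". Admission and discharge dates go to the analysts in structured EHR datasets. Section 6.5 defines the analysed patients as the eligible patients seen at any of the 24 clinics, so both arms are covered. Section 10.3.1 lists hospitalization among the criteria for a serious adverse event.

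On oversight, section 10.2 says: "The DSMB will act in an advisory capacity to the NIH to monitor participant safety".

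**The concern.** The reason given for not looking for harms is that it would take patient contact and chart review. A count of admissions from structured fields needs neither, and section 11 already plans to hold those fields for both arms. The protocol says why it wants inpatient data, then never uses them in an endpoint or an analysis.

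At stake is the reading of a positive result. Section 6.5 treats more intensification and lower pressure as success. Without a prespecified harm outcome, a fall in systolic pressure could not be set against any randomized estimate of what the tools did to admissions. The expectation of no excess would rest on other trials. Passive reports cannot fill the gap. They have no denominator, and they come from providers who know their arm (section 5.2).

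**Working it through.** **1. Sections set side by side**

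| Place | Content on harms |
|---|---|
| Section 2, objectives and endpoints | none |
| Section 6.3, data-collection table | none (systolic pressure, drug dosage, outpatient contacts) |
| Section 6.5, endpoints | none; intensification is a secondary outcome |
| Section 9.3, analyses | no between-arm safety analysis |
| Section 10.3.1 | hospitalization is a serious adverse event criterion |
| Section 10.3.3 | passive reports only |
| Section 11 | inpatient extract, stated purpose includes hospitalizations |

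The gap is one of prespecification: the data are planned, the outcome is not.

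**2. The plan's own power figure**

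Inputs from sections 5.2 and 9.2: 24 clinics in equal proportions, 49,395 patients, difference 5.0 mmHg, SD 13.5, ICC 0.1, alpha 0.05 (taken as two-sided).

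- Mean cluster size m = 49,395/24 = 2,058.1; patients per arm = 24,697.5
- Design effect = 1 + (m − 1) × 0.1 = 206.7
- Effective n per arm = 24,697.5/206.7 = 119.5
- SE = 13.5 × √(2/119.5) = 1.747 mmHg; 5.0/1.747 = 2.86
- Power = Φ(2.86 − 1.96) = 81.7%

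This reproduces the stated power of more than 80% (normal approximation, equal cluster sizes). The same structure is used below.

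**3. Precision of a by-arm hospitalization comparison**

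The documents give no event rate and no ICC for harms. Both are assumptions: control rate p of 1-3%, ICC 0.001-0.01, with 0.1 shown because it is the only ICC in the plan.

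The detectable difference d at 80% power, with each arm's own variance and 24 − 2 = 22 degrees of freedom, solves

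d = 2.93 × √{ DE/24,697.5 × [p(1 − p) + (p + d)(1 − p − d)] },

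where DE = 1 + 2,057.1 × ICC and 2.93 = 2.074 + 0.858 (97.5th and 80th percentiles of t with 22 df). DE is 3.06, 21.6 and 206.7 for ICC 0.001, 0.01 and 0.1.

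| Control rate | ICC 0.001 | ICC 0.01 | ICC 0.1 |
|---|---|---|---|
| 1% | 0.51 points (RR 1.51) | 1.63 (RR 2.63) | 8.20 (RR 9.2) |
| 2% | 0.70 (RR 1.35) | 2.10 (RR 2.05) | 9.28 (RR 5.6) |
| 3% | 0.84 (RR 1.28) | 2.46 (RR 1.82) | 10.2 (RR 4.4) |

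Over the assumed range with ICC up to 0.01, d is 0.51-2.46 points and the risk ratio 1.28-2.63. At a higher control rate of 5% the corresponding ratios are 1.21, 1.60 and 3.3.

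**4. What passive reports can show**

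The share of events reported is unknown, so no rate can be formed. As an illustration, take a true risk of 1% in both arms, or 247 events each. If 10% were reported in one arm and 5% in the other, the team would see about 24.7 and 12.3 reports, an apparent ratio of 2.0 with no true difference. These reporting shares are invented; the documents do not show that reporting would differ.

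**The case against.** The best defence is that section 10.3.3 calls prospective tracking infeasible, and nothing in section 11 disproves that. Section 6.5 has the data extracted retrospectively at the end of the study, so the extract does not permit real-time monitoring. This stands. What the extract undercuts is the claim that chart review and contact would be needed, and only for a retrospective comparison.

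Readers might infer four stronger things that the documents do not support.

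- That the DSMB will have no data by arm. The text is silent on this. Section 10.2 has the board review study data, section 10.3.3 lets it ask for different reporting, and pages following the DSMB appendix were not available for review.
- That reports will be unequal between arms. Contact details are not restricted to one arm. Only intervention providers receive tool training and are interviewed (sections 6.2.1 and 6.3.1), and providers are unblinded, so differential reporting is plausible. It is a risk, not a demonstrated fact.
- That the missing comparison would show whether intensification causes harm. Randomization is to the EHR tools, so a comparison by arm estimates their effect, not that of intensification itself.
- That section 10.3.2 literally expects no adverse events among 49,395 patients. Its next sentence speaks of medication-related events at routine-care rates or below. This is loose wording.

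A fair point also limits the remedy. Intervention clinics get charting templates and can order nurse blood pressure checks (sections 6.2.3 and 6.2.4). More visits and documentation could raise coded hypotension or bradycardia there without more true harm. All-cause hospitalization is less exposed to this.

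**Conclusion.** The point holds as a gap in prespecification. The plan as written produces no randomized comparison of harms of the EHR intervention, although section 11 plans the data for at least one such comparison. The harm outcome could still be examined after the fact, but an unplanned query carries less weight than a stated outcome.

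The comparison would be informative but not decisive. Under the assumed rates and ICCs up to 0.01, it detects differences of about 0.5-2.5 points. If clustering of admissions were as strong as the ICC of 0.1 assumed for systolic pressure, only risk ratios of about 4-9 would be detectable. The calculation assumes equal cluster sizes and all 49,395 patients contributing 12 months of follow-up. The variable list is in attachments not available for review, so it is not confirmed that diagnosis codes are included; admission and discharge dates are stated in section 11.

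**What to change.** - **Sections 6.5 and 9.3:** add a retrospective safety outcome, all-cause hospitalization within 12 months of identification. Report counts and proportions by arm, with a risk difference and 95% confidence interval that allows for clustering by clinic, from the end-of-trial extract. The log-link Poisson GEE in section 9.3 yields a ratio, so state how the difference will be obtained, for example with an identity link.
- **Interpretation:** state that a non-significant result will not be read as absence of harm.
- **Supportive outcomes:** if the codes are in the extract, coded events matching the risks named in section 7 may be added, with the caveat about extra visits and documentation in the intervention arm.
- **Section 10.3.3:** amend to say that prospective tracking is not done, and that passive reports are supplemented by this retrospective comparison.

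The cost is one outcome definition and one table for hospitalization, plus a code list if supportive events are added. No patient contact, chart review or interim extract is needed. The limitation to declare is that network data miss admissions elsewhere and mild events.

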## **11. Privacy and Confidentiality**

- Study procedures will be conducted in a private setting
- Only data and/or specimens necessary for the conduct of the study will be collected

- Data collected (paper and/or electronic) will be maintained in a secure location with appropriate protections such as password protection, encryption, physical security measures (locked files/areas)
- Specimens collected will be maintained in a secure location with appropriate protections (e.g. locked storage spaces, laboratory areas) – **N/A**
- Data and specimens will only be shared with individuals who are members of the IRB-approved research team or approved for sharing as described in this IRB protocol
- Data and/or specimens requiring transportation from one location or electronic space to another will be transported only in a secure manner (e.g. encrypted files, password protection, using chain-of-custody procedures, etc.)
- All electronic communication with participants will comply with Mass General Brigham secure communication policies
- Identifiers will be coded or removed as soon as feasible and access to files linking identifiers with coded data or specimens will be limited to the minimal necessary members of the research team required to conduct the research
- All staff are trained on and will follow the Mass General Brigham policies and procedures for maintaining appropriate confidentiality of research data and specimens
- The PI will ensure that all staff implement and follow any Research Information Service Office (RISO) requirements for this research
- Additional privacy and/or confidentiality protections

Advocate investigators will extract data that contains patient health information (PHI) including MRN, first name, last name, date of birth, encounter dates, and Zip Codes. To protect against the risk of inappropriate disclosure of personal health information, only limited data will be shared with study collaborators at Mass General Brigham (MGB) who will oversee and conduct the analysis with insights from the Advocate team. The only PHI that will be shared with the BWH study investigators outside of Advocate are dates (e.g., date of birth, admission/discharge dates, and dates of medication fills), which are necessary to evaluate exposures and outcomes retrospectively. No other study investigators outside of BWH will receive any PHI. Advocate will then disclose HIPAA-limited datasets encrypted by a study key only known to the Advocate investigators to conduct the analyses. These datasets will consist of structured information from the EHR. Sharing this information will be necessary to assess the impact of the interventions.

The electronic data stored at Advocate will be safeguarded by state-of-the-art security protocols. All patient-specific information will be collected by querying Advocate's inpatient and outpatient databases; inpatient data will be necessary to evaluate outcomes such as hospitalizations. Identified patient information will be recorded on a password-protected electronic spreadsheet, with each patient assigned a specific study number. All identifiers (excluding dates) linked to study numbers will be locked and stored separately from the data analysis spreadsheet. The coded spreadsheet will also be stored on a password-protected computer in a locked office with access limited to study investigators only. Only the limited dataset will be utilized for analyses. All identifiers will be destroyed after completion of data analysis. Only study team members will have access to study related documents. All investigators have completed CITI training.

Mass General Brigham (MGB) has computer networks in place that employ up to date virus protection software and enable password-protected access only to study investigators. All data transfers between the organizations will be accomplished using secure file transfer protocols. To ensure the confidentiality

and security of all data, the research team operates a secure, state-of-the-art computing facility housed at MGB Healthcare's data center. The MGB data center is a secure facility that houses both computing environments as well as clinical systems and electronic medical records for several large hospitals in Eastern Massachusetts. Entry into the computer room requires staffed computer room security. The Division's computers are connected to the MGB networking backbone with 10 gigabit-per-second fiber links. Network security is overseen by electronic medical records systems to the research team's data. All data are transmitted to programmers' workstations in an encrypted state. Backups are created using the current Department of Defense standard for data security and are stored in a locked facility. The redundancy, extensive data power, and security of our computer facility confirm our capacity to collect and manage data and ensure confidentiality for all project participants.

